13.5 Monitoring Rules

The study will be referred to the DSMC for review of dosing and toxicity at the first occurrence of a toxic death.

A Simon's two-stage group sequential design will be used to determine if there is sufficient evidence of efficacy to warrant further investigation of clofarabine.

Rule A - Two-stage stopping rule for response in Stratum 1

Stage 1: Accrue 13 evaluable participants. If 7 or fewer respond, then there is insufficient evidence to support further study of clofarabine in this cohort, and the study will be closed to further accrual. We would also close the trial if it became apparent prior to the accrual of all 13 that we would never achieve the 8 responders. If 8 or more out of 13 are responders, then proceed to stage 2.

Stage 2: A total of 20 evaluable patients will be studied. If 13 or fewer respond, then there is insufficient evidence to support further study of clofarabine in this cohort. If 14 or more are responders, then there is sufficient evidence to warrant further investigation of clofarabine within this cohort.

This rule has 91% power to detect a 27% difference (53% under the null to 80% under the alternative), with $\alpha = 0.093$. If the response rates were actually higher, there would be even greater power to detect a 27% difference, for example 63% versus 90%.

Rules for monitoring for toxicity associated with chemotherapy

The study will be monitored to ensure the therapy can be delivered as planned ('chemotherapy feasibility'). Toxicities will be graded according to CTCAE version 4.0. Unacceptable toxicity will be defined as grade 5 toxicity and Grade 3 or 4 non-hematological toxicity that are possibly, probably, or definitely related to Clofarabine, with the specific exceptions of the following Grade 3 toxicities: anorexia, weight loss, nausea, vomiting, fatigue, mucositis, diarrhea, fever, electrolyte/metabolic abnormalities, menorrhagia, and

CONFIDENTIAL

This document is confidential. Do not disclose or use except as authorized.

infection. Because all patients, regardless of stratum, receive the same treatment with the standard dose of clofarabine (25 mg/m²/d), the stopping rule for toxicity will be applied to the overall cohort, i.e., combining Stratum 1 and Stratum 2. The toxicity monitoring rule will be applied to the first 25 evaluable participants, as this will provide sufficient evidence of safety/feasibility for the balance of the trial's accrual.

Rule B – Three-stage stopping rule for toxicity events

Stage 1: Accrue 7 evaluable participants. If at any time 2 or more participants experience a toxicity-event, enrollment will be suspended for DSMB review of dosage modifications or stopping the trial. If 1 or fewer have a toxicity-event, then proceed to stage 2.

Stage 2: Accrue an additional 8 evaluable participants for a total of 15. If at any time 3 or more participants experience a toxicity-event, enrollment will be suspended for DSMB review of dosage modifications or stopping the trial. If 2 or fewer have a toxicity-event, then proceed to stage 3.

Stage 3: Accrue an additional 10 evaluable participants for a total of 25. If 7 or more participants experience a toxicity-event, then there is insufficient evidence to support chemotherapy feasibility. If 6 or fewer have a toxicity-event, then there is sufficient evidence that the therapy can be delivered as planned, and this evidence supports continuation until the accrual goal for this trial is reached.

If all 25 participants are evaluated and the true toxicity-event rate is 5%, the therapy will be considered tolerable with a probability of 0.94. If all 25 participants are evaluated and true toxicity-event rate is 30%, the therapy will be considered tolerable with a probability of 0.1.

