11.2 Safety Meetings

The DF/HCC Data and Safety Monitoring Committee (DSMC) will review and monitor toxicity and accrual data from this trial. The committee is composed of clinical specialists with experience in oncology and who have no direct relationship with the study. Information that raises any questions about participant safety will be addressed with the Principal Investigator and the Lead Site study team.

The DSMC will meet quarterly and/or as often as necessary, as determined by the DSMC, if required to review toxicity and accrual data. Information to be provided to the committee may include: up-to-date participant accrual; current dose level information; DLT information; all grade 2 or higher unexpected adverse events that have been reported; summary of all deaths occurring within 30 days for Phase I or II protocols; for gene transfer protocols, summary of all deaths while being treated and during active follow-up; any response information; audit results, and a summary provided by the study team. Other information (e.g. scans, laboratory values) will be provided upon request.

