13.2 Sample Size/Accrual Rate

Twenty evaluable participants in Stratum 1 will be required in order to have sufficient power to address the study's primary objective. To account for participants who enroll and are subsequently determined to be ineligible or unevaluable, a total of up to 25 participants may be enrolled in order to obtain 20 evaluable patients. At an estimated accrual rate of 10 participants per year, the accrual goal of 20 evaluable participants can be achieved in less than 4 years. It is estimated that up to 10 patients per year meeting the eligibility criteria for Stratum 2 are seen across all study sites (personal communication from [name]). Therefore, the estimated accrual rate of Stratum 2 patients is up to 5 patients per year, which allows for up to 20 patients in Stratum 2, though realistically, fewer of these rare patients are anticipated to be enrolled. We estimate a total study accrual of up to 45 patients (25 in Stratum 1, and 20 in Stratum 2).

Once the accrual goal of eligible patients for a given stratum is reached (with a 5-patient overage to account for potentially ineligible patients), that stratum will be closed to accrual. Once the accrual goal of evaluable patients is met within Stratum 1, the overall study will be closed even if fewer than 20 patients have been enrolled in Stratum 2. In the unlikely event that 20 patients are enrolled on Stratum 2 before Stratum 1 has met its accrual goal, Stratum 2 will be closed to accrual.

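### Section 13.5 mandates DSMC referral only at the first toxic death; a later toxic death that crosses no Rule B suspension limit has no event-driven DSMC review

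*Combined protocol and SAP*

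**What the plan says.** Section 13.5 has one trigger specific to deaths: "The study will be referred to the DSMC for review of dosing and toxicity at the first occurrence of a toxic death". It carries no accrual limit, but it operates once.

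The only other event-driven committee review is Rule B in the same section, which pools both strata:

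- Stage 1 (first 7): "If at any time 2 or more participants experience a toxicity-event, enrollment will be suspended for DSMB review".
- Stage 2 (first 15): "If at any time 3 or more participants experience a toxicity-event, enrollment will be suspended for DSMB review".
- Stage 3 (25): "If 7 or more participants experience a toxicity-event, then there is insufficient evidence to support chemotherapy feasibility". Here there is no running suspension and no mention of committee review.
- Coverage: "The toxicity monitoring rule will be applied to the first 25 evaluable participants".

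Section 13.2 allows up to 45 participants (25 in Stratum 1 and 20 in Stratum 2) and adds: "Once the accrual goal of evaluable patients is met within Stratum 1, the overall study will be closed".

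Section 11.2 sets the routine oversight: "The DSMC will meet quarterly and/or as often as necessary, as determined by the DSMC". A summary of deaths within 30 days is among the listed items, but the list opens with "Information to be provided to the committee may include". Section 13.5 says DSMC for the death trigger and DSMB in Rule B; I take these to be the same committee.

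**The concern.** A second or third treatment-related death is the observation most likely to change the view of dosing formed after the first. The plan treats the first such death as serious enough for its own referral, over and above the quarterly cycle, and gives no reason why the next should need less. Rule B does not fill the space, because it counts toxicity-events and gives a death no extra weight.

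Three situations fall outside both triggers:

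1. The second event is a second death among participants 8 to 15, with at most one event in the first 7. The Stage 2 limit of three is not reached, whatever happens afterward.
2. A later death occurs among participants 16 to 25, where Stage 3 has only its reading at 25.
3. A later death occurs after participant 25, when Rule B no longer applies.

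At stake is whether the independent committee looks at dosing promptly because of that death, or at its next scheduled meeting unless someone calls it sooner.

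**Working it through.** **Reproducing the plan's figures.** Write b(n,x) for the binomial probability of x events in n at event rate p. Rule B passes with probability Σ b(7,x)·b(8,y)·b(10,w) over x ≤ 1, x+y ≤ 2, x+y+w ≤ 6. This gives 0.937 at 5% and 0.096 at 30%, matching the stated 0.94 and 0.1. Rule B's published properties are not in question.

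**Assumptions for the gap.**

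- The toxic-death rate p is 2%, 5% or 10%, and the rate of non-fatal toxicity-events q is 0%, 5%, 10% or 15%. All are illustrative.
- Each toxic death counts as a toxicity-event. Section 13.3 defines the event as clofarabine stopped for toxicity and does not name death; section 13.5 lists grade 5 as unacceptable toxicity. Counting every death favors the plan.
- No action follows the first referral, and outcomes are known in participant order.

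**No other events (q = 0).** A second death goes unreferred exactly when there are two or more deaths in N participants but not two or more in the first 7:

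G(N) = P(≥2 of N) − P(≥2 of 7), where P(≥2 of n) = 1 − (1−p)^n − np(1−p)^(n−1).

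| p | P(≥2 of 7) | P(≥2 of 25) | G(25) | P(≥2 of 45) | G(45) |
|---|---|---|---|---|---|
| 2% | 0.0079 | 0.0886 | 0.081 | 0.2271 | 0.219 |
| 5% | 0.0444 | 0.3576 | 0.313 | 0.6650 | 0.621 |
| 10% | 0.1497 | 0.7288 | 0.579 | 0.9476 | 0.798 |

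**With non-fatal events.** Add participants one at a time: death (p), other toxicity-event (q), neither (1−p−q). A path counts once it has a death that is not the first and does not itself cross a limit. It stops when the event total reaches 2 within 7, 3 within 15, or 7 within 25; a path already counted stays counted. Probability of at least one unreferred later death:

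| N | q | p = 2% | p = 5% | p = 10% |
|---|---|---|---|---|
| 25 | 0% | 0.08 | 0.31 | 0.58 |
| 25 | 5% | 0.06 | 0.22 | 0.39 |
| 25 | 10% | 0.04 | 0.15 | 0.24 |
| 25 | 15% | 0.02 | 0.09 | 0.14 |
| 45 | 0% | 0.22 | 0.62 | 0.80 |
| 45 | 5% | 0.18 | 0.49 | 0.58 |
| 45 | 15% | 0.08 | 0.21 | 0.22 |

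**Which N applies.** Forty-five is the ceiling. At the planned 10 per year in Stratum 1 and up to 5 in Stratum 2, filling Stratum 1 with 20 to 25 participants takes 2 to 2.5 years, so total accrual is 2 × 15 = 30 to 2.5 × 15 = 37.5. With no Stratum 2 accrual the total is 20 to 25 and situation 3 does not arise. Nor does it arise if Rule A closes the study at 13 Stratum 1 participants (about 13/10 × 15 = 19.5 in all). That closure has probability P(X ≤ 7 of 13) = 0.63 at a 53% response rate and 0.03 at 80%.

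**Delay.** Expected enrollment over a full quarter is 10/4 = 2.5 to 15/4 = 3.75. A death falling at random within the quarter leaves half of that on average: 1.25 to 1.9.

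**The case against.** Referring once and letting the committee choose its later triggers is a legitimate design. After the first toxic death the DSMC has been asked about dosing and toxicity, may set its own conditions, and can meet whenever it judges necessary.

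A reader might infer that later toxic deaths go unreported, or that nobody can act on them. The documents do not support that:

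- Every on-treatment fatal event is expedited to the principal investigator within one business day (10.2). It also goes to the IRB (10.5), to the supplier (10.8), and to FDA and Health Canada where their criteria are met (10.6).
- Sites must notify the principal investigator or sponsor at once of life-threatening complications or toxicities (5.7, 17.3.9), and temporary holds take effect immediately (17.3.2).
- An expected reaction that proves fatal counts as unexpected unless the labeling says it may be fatal (10.1), so many toxic deaths would fit two of the items listed for the DSMC in 11.2.
- The SAE log is reviewed on monthly calls (17.5.1.8).

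A reader might also note that six toxic deaths in 25, with at most one in the first 7 and two in the first 15, would literally pass Rule B, and infer that the trial would carry on regardless. That does not follow either, since the committee and the sponsor keep discretion throughout.

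These points stand and limit the weight of the finding. They do not remove it: none of these provisions requires the DSMC to review dosing because a second or later toxic death has occurred. The objection that the death rates are arbitrary also stands, so the probabilities are illustrations and not forecasts.

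**Conclusion.** The point holds as a narrow gap in a mandated trigger, and it is minor. It involves no conflict with another section and no effect on any analysis or error rate. Its practical size is the interval to the next quarterly meeting, and only if no one convenes the DSMC sooner.

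How often the gap would open depends almost entirely on rates the documents do not give. Across the assumed rates the probability runs from 0.02 to 0.58 in 25 participants and from 0.08 to 0.80 at the ceiling of 45. The high ends require a 10% toxic-death rate, no non-fatal toxicity-events, and no DSMC action after the first death; action at that point would lower every figure. If some toxic deaths were not counted as toxicity-events under 13.3, fewer would reach a Rule B limit and the gap would be wider.

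**What to change.** In section 13.5, replace the restriction to the first occurrence with: *at each toxic death, whenever it occurs (including after the 25th evaluable participant and after accrual closes)*. Add that the DSMC decides at each referral whether to hold enrollment or treatment.

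The reference to the period after accrual matters. Six cycles of 28 to 42 days (section 5) keep the last participant on the regimen for 6 × 28 = 168 to 6 × 42 = 252 days, that is 24 to 36 weeks. The present sentence covers a first toxic death in that period, so wording tied to accrual would narrow existing protection.

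Rules A and B and their operating characteristics are untouched. The cost is one sentence, a few ad hoc reviews by a committee that already exists, and possibly a short pause. The expected number of reviews beyond the first, if nothing stops the trial, is np − [1 − (1−p)^n]. For n = 30 to 38 this is 0.15 to 0.22 at a 2% death rate, 0.7 to 1.0 at 5%, and 2.0 to 2.8 at 10%.

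### Stage 3 of toxicity Rule B carries no running trigger and no enrolment action, so a trial that reaches its failing count of 7 before the 25th participant keeps enrolling under the rule as written

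*Combined protocol and SAP*

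**What the plan says.** All of this stands in Section 13.5, Rule B, which pools both strata and covers the first 25 evaluable participants.

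- Stage 1: "Accrue 7 evaluable participants. If at any time 2 or more participants experience a toxicity-event, enrollment will be suspended for DSMB review".
- Stage 2: "Accrue an additional 8 evaluable participants for a total of 15". Then: "If at any time 3 or more participants experience a toxicity-event, enrollment will be suspended for DSMB review of dosage modifications or stopping the trial".
- Stage 3: "Accrue an additional 10 evaluable participants for a total of 25". The failing branch is "If 7 or more participants experience a toxicity-event, then there is insufficient evidence to support chemotherapy feasibility". The passing branch is "If 6 or fewer have a toxicity-event, then there is sufficient evidence that the therapy can be delivered as planned", and the plan adds that this supports going on to the accrual goal.

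The plan gives a 0.94 chance of calling the therapy tolerable at a true rate of 5%. For the unfavourable case it says: "If all 25 participants are evaluated and true toxicity-event rate is 30%, the therapy will be considered tolerable with a probability of 0.1".

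Section 13.2 allows up to 45 participants in total. Section 13.6 makes Rule B the analysis for secondary objectives 1.4.b and 1.4.c.

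**The concern.** Stages 1 and 2 each have two working parts: a trigger that applies as events occur, and an action on enrolment. Stage 3 has neither. Its count is read when 25 participants are in, and failing yields a conclusion about feasibility with no instruction to suspend, review or close.

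From participant 16 on, Rule B therefore contains no hold on enrolment, even when the seventh event has already settled the Stage 3 result. Further participants would be enrolled into a regimen that the rule can now only judge not feasible. Stage 3 is also the last look under Rule B. Up to 45 − 25 = 20 more participants may follow it, so the consequence of failing should be explicit.

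**Working it through.** **Inputs (Section 13.5).** Stage sizes are 7, 8 and 10. Cumulative failing counts are 2, 3 and 7. Design rates are 5% and 30%. Let E(m) be the number of toxicity-events among the first m participants, with independent participants and a common rate p.

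**Step 1: reproduce the stated figures.** Count a Stage 1 or 2 suspension as not tolerable. Then

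P(tolerable) = P[E(7) ≤ 1, E(15) ≤ 2, E(25) ≤ 6].

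At p = 0.30:

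- First 7: P(0) = 0.08235 and P(1) = 0.24706, so Stage 1 stops 1 − 0.32941 = 0.6706.
- Next 8: P(0) = 0.05765, P(1) = 0.19765, P(2) = 0.29648.
- Entering Stage 3 with 0 events: 0.08235 × 0.05765 = 0.00475.
- With 1 event: 0.08235 × 0.19765 + 0.24706 × 0.05765 = 0.03052.
- With 2 events: 0.08235 × 0.29648 + 0.24706 × 0.19765 = 0.07325.
- Reaching Stage 3: 0.1085. Stage 2 stops 1 − 0.6706 − 0.1085 = 0.2209.
- Failing Stage 3 needs at least 7, 6 or 5 events in the last 10 (probabilities 0.0106, 0.0473, 0.1503): 0.00005 + 0.00145 + 0.01101 = 0.0125.
- Tolerable: 0.1085 − 0.0125 = **0.0960** (stated 0.1).

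The same sum at p = 0.05 gives **0.9368** (stated 0.94).

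Other readings do not fit. A single look at 25 with a cut of 7 gives 0.9998 and 0.341. Conditioning on reaching Stage 3 gives 1.000 and 0.885. The stated figures are therefore unconditional over the three stages, although the sentence speaks of all 25 being evaluated.

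**Step 2: does a running trigger at 7 alter them?** E(m) never falls, so E(m) ≥ 7 for some m ≤ 25 exactly when E(25) ≥ 7. Both figures stay as they are.

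**Step 3: how often would it act before participant 25?** It acts early when E(24) ≥ 7.

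*(a) Earlier suspensions end the trial, p = 0.30.* From 0, 1 or 2 events, the trial needs at least 7, 6 or 5 among the next 9 (probabilities 0.0043, 0.0253, 0.0988):

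0.00475 × 0.0043 + 0.03052 × 0.0253 + 0.07325 × 0.0988 = 0.00002 + 0.00077 + 0.00724 = **0.008**.

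*(b) The board lets a suspended trial resume, p = 0.30 unchanged.*

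- 3 events at participant 15: P(at least 4 of the next 9) = **0.27**.
- 4 events at participant 15: P(at least 3 of the next 9) = **0.54**.

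At p = 0.05 the same two probabilities are 0.0006 and 0.0084, so the trigger would seldom interrupt a trial at the rate the plan treats as acceptable.

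**Step 4: the cut itself, as information.** Chance of being called tolerable, with Stages 1 and 2 unchanged and a suspension counted as rejection:

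| True rate | No Stage 3 cut | Cut of 7 (plan) | Cut of 5 |
|---|---|---|---|
| 5% | 0.9368 | 0.9368 | 0.9352 |
| 10% | 0.7626 | 0.7622 | 0.7428 |
| 15% | 0.5471 | 0.5445 | 0.4936 |
| 20% | 0.3518 | 0.3449 | 0.2752 |
| 25% | 0.2049 | 0.1938 | 0.1297 |
| 30% | 0.1085 | 0.0960 | 0.0519 |

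Across these rates the cut of 7 adds at most 0.1085 − 0.0960 = 0.0125 to rejection.

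**The case against.** **Rule B is headed a stopping rule, and only its passing branch supports continuing.** This stands in part. A sensible team would not carry on to 45 after failing, and a reader who infers that the plan permits this goes further than the text. But the heading does not say when enrolment halts or who reviews the result, and Stages 1 and 2 do.

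**The Stage 2 trigger might be meant to run on.** Its text is "If at any time 3 or more participants experience a toxicity-event, enrollment will be suspended", which could be read as still in force after participant 15. That does not fit a Stage 3 that passes up to 6 events. A cut of 3 kept through participant 25 would also give 0.8568 at 5% and 0.0084 at 30%, not 0.94 and 0.1.

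**Participants 16 to 25 are not unmonitored.** Correct, and the documents would not support saying otherwise. Section 13.5 refers the first toxic death to the DSMC, Section 11.2 provides quarterly or more frequent review, Section 10.2 requires SAE notice within 1 business day, and Section 17.5.1.8 reviews SAE logs on monthly calls. None of these is an automatic hold on enrolment for non-fatal toxicity-events.

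**The trigger would almost never act.** True if suspensions end the trial. A seventh event by participant 20 would need 2 events at participant 15 and then five in a row: 0.07325 × 0.3⁵ = 0.0002 at a 30% rate. But the suspension text names dosage modification as one outcome of review, so a trial may resume with 3 or more events, and Rule B then offers no later hold.

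**Conclusion.** The point holds as a gap in the wording of the monitoring rule. Stage 3 lacks the running trigger and the enrolment action of Stages 1 and 2, so reaching the failing count early does not pause enrolment. The effect is small on the plan's own model and material after a resumed suspension (Step 3).

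These sizes assume independent participants, a constant event rate (including after any dosage change) and each outcome known before the next enrolment. Treatment can last six cycles, so real counts will lag behind accrual and the trigger would act somewhat later. The documents do not say how often the board would allow resumption, so the two cases in Step 3 are shown separately and not averaged.

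A reader might infer that the cut of 7 is wrong and should be 5, because Stage 3 rejects so little. The documents do not support that. The rule delivers the two probabilities it states, and the plan sets no target between 5% and 30%. A cut of 5 would roughly halve acceptance at 30% (0.096 to 0.052) and still give 0.935 at 5%, but it lowers acceptance from 0.545 to 0.494 at 15% and from 0.345 to 0.275 at 20%. That is a trade-off for the sponsor and safety committee, not an error.

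**What to change.** Reword Stage 3 to match Stages 1 and 2: once 7 participants have had a toxicity-event, at whatever point up to the 25th evaluable participant, enrolment is suspended for DSMB review. Keep the passing branch at 6 or fewer of 25. State the same action for a seventh event that first appears at the final count.

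The cost is one sentence and an IRB-approved amendment (Section 12.1). No participants are added, and the stated 0.94 and 0.1 stand. The sponsor and safety committee may look at the cut when they make the change. If they alter it, the acceptance probabilities must be restated, and the feasibility conclusion for objectives 1.4.b and 1.4.c would rest on the new cut.

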13.6 Statistical Methods to Address Objectives

Objective 1.3 - Monitoring Rule A will be used to address primary objective 1.3. The analysis will include all evaluable Stratum 1 participants. In addition, a 95% confidence interval will be placed on the response rate.

Secondary Objective 1.4.a – Descriptive analyses using the methods of Kaplan and Meier (with standard errors per Peto) will be performed to calculate the PFS and OS within each stratum and overall. Lifetables will also be constructed.

Secondary Objective 1.4.b – Monitoring Rule B will be used to address secondary objectives 1.4.b and 1.4.c. In addition, a descriptive tabulation of the proportion of participants reporting grade 3 and higher toxicity, separately by stratum (1 and 2) and by CTC toxicity code, will be generated for all evaluable patients. A given participant will be counted only one time per toxicity code at the maximum grade regardless of the number of times that participant experienced the toxicity.

Secondary Objective 1.4.c – Within Stratum 2 and within subgroups of Stratum 2, we will calculate the proportion of evaluable patients who are responders, and place 95% confidence intervals on these proportions. A descriptive tabulation of the proportion of participants reporting grade 3 and higher toxicity, by CTC toxicity code, will be generated for Stratum 2 patients. A given participant will be counted only one time per toxicity code at the maximum grade regardless of the number of times that participant experienced the toxicity.

CONFIDENTIAL

This document is confidential. Do not disclose or use except as authorized.

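### Do Rule B's 0.94 and 0.1 conflict with the condition that all 25 participants are evaluated?

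*Combined protocol and SAP*

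**What the plan says.** Section 13.5 sets out Rule B, headed "Three-stage stopping rule for toxicity events", for both strata combined: "the stopping rule for toxicity will be applied to the overall cohort". It covers the first 25 evaluable participants.

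- **Stage 1** ("Stage 1: Accrue 7 evaluable participants"): with 2 or more toxicity-events, "enrollment will be suspended for DSMB review of dosage modifications or stopping the trial". With 1 or fewer, the trial goes on to Stage 2.
- **Stage 2** (8 more, 15 in total): the same suspension applies with 3 or more events. With 2 or fewer, the trial goes on to Stage 3.
- **Stage 3** (10 more, 25 in total): 7 or more events means feasibility is not supported; 6 or fewer means it is.

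Two operating characteristics follow: "If all 25 participants are evaluated and the true toxicity-event rate is 5%, the therapy will be considered tolerable with a probability of 0.94" and "If all 25 participants are evaluated and true toxicity-event rate is 30%, the therapy will be considered tolerable with a probability of 0.1".

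Section 13.6 gives the rule its role in the analysis: "Monitoring Rule B will be used to address secondary objectives 1.4.b and 1.4.c". Section 13.2 allows accrual to end before 25 evaluable participants are reached: once Stratum 1 has its 20 evaluable patients, "the overall study will be closed even if fewer than 20 patients have been enrolled in Stratum 2".

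**The concern.** Both probabilities are introduced as holding when all 25 participants are evaluated. A trial that stops at Stage 1 or 2 never evaluates 25, so a literal reader removes those trials before computing anything. Yet at a 30% event rate the early stages are where nearly all the unfavourable results arise, and without them the probability cannot be as low as 0.1.

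A second feature adds to the doubt. A Stage 1 or 2 crossing leads to suspension and review, and the rule attaches no tolerability verdict to it. Rule A, in the same section, says outright that the study closes when its first-stage boundary is missed.

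If the 0.1 were meant to describe trials that resume after review and reach 25 participants, it would understate the chance of calling a toxic regimen feasible. Because Rule B is the named method for the feasibility objective, the error rate would then be wrong for a secondary conclusion of the trial.

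**Working it through.** **Inputs, all from section 13.5.** Cumulative stage sizes 7, 15 and 25. Proceed with at most 1 event in 7 and at most 2 in 15. Favourable verdict with at most 6 in 25. True rates p = 0.05 and p = 0.30. Participants are treated as independent with a common rate. Counts are cumulative, so checking at any time within a stage gives the same result as checking at its end.

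**Step 1. Reproduce the plan's figures from the gated rule.** Let X7, X15 and X25 be the cumulative event counts. The probability of a favourable verdict is P(X7 ≤ 1, X15 ≤ 2, X25 ≤ 6).

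At p = 0.30:

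- Stage 1: P(X7 = 0) = 0.7^7 = 0.0824 and P(X7 = 1) = 7 × 0.3 × 0.7^6 = 0.2471. The gate is passed with probability 0.3294.
- Stage 2: the next 8 participants have 0, 1 or 2 events with probability 0.0576, 0.1977 and 0.2965. Combining these with Stage 1:
  - X15 = 0: 0.0824 × 0.0576 = 0.0047
  - X15 = 1: 0.0824 × 0.1977 + 0.2471 × 0.0576 = 0.0305
  - X15 = 2: 0.0824 × 0.2965 + 0.2471 × 0.1977 = 0.0732
  - Both gates passed: 0.1085
- Stage 3: the last 10 participants may have at most 6, 5 or 4 events respectively, with probability 0.9894, 0.9527 and 0.8497. The total is 0.0047 × 0.9894 + 0.0305 × 0.9527 + 0.0732 × 0.8497 = **0.096**, published as 0.1.

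At p = 0.05 the same steps give 0.9556 after Stage 1, 0.9368 after Stage 2 and **0.937** at the end, published as 0.94.

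**Step 2. See where the unfavourable probability comes from at 30%.** Stage 1 crossing 1 − 0.3294 = 0.671; Stage 2 crossing 0.3294 − 0.1085 = 0.221; Stage 3 failure without a crossing 0.1085 − 0.0960 = 0.0125. The sum is 0.904 = 1 − 0.096. The published figure therefore counts every early crossing as not tolerable.

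**Step 3. Compute the literal readings of the condition.**

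| Reading | p = 0.05 | p = 0.30 |
|---|---|---|
| Gated rule, unconditional | 0.937 | 0.096 |
| 25 reached with no crossing: gated value ÷ P(both gates passed) | 0.99999 | 0.0960 / 0.1085 = 0.885 |
| 25 evaluated whatever the crossings, unchanged rate: P(X25 ≤ 6) | 0.9998 | 0.341 |
| Published | 0.94 | 0.1 |

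The 0.341 consists of the gated 0.096 plus 0.245 from trials that cross a boundary early but would finish with 6 or fewer in 25.

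**Step 4. Try other versions of the rule.** Ignoring a Stage 1 crossing gives 0.964 and 0.112. Ignoring a Stage 2 crossing gives 0.956 and 0.191. Applying the Stage 2 limit to the 8 new participants only gives 0.950 and 0.144. None of these rounds to both published figures; the gated rule does.

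**The case for a change.** The strongest case for an edit is that the words as printed do not describe the numbers. At 30%, 0.891 of trials (0.671 + 0.221, allowing for rounding) cross early. If a crossing is final, those trials never evaluate 25 participants, so the stated condition excludes the very trials that make the figure 0.1. If a crossing is not final, the plan does not say what verdict applies to a trial that resumes and ends with 6 or fewer events in 25. At an unchanged 30% rate that adds 0.245 to the chance of a favourable finding.

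Part of this stands. The lead-in is imprecise, and no sentence states the feasibility verdict for a trial that crosses and then resumes.

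The rest carries less weight:

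- The stage gates already define the route to a favourable verdict. Stage 3 is entered from Stage 2 with 2 or fewer events, and Stage 2 from Stage 1 with 1 or fewer. No text sends a crossed trial on to the 25-participant test.
- The review is of dosage modifications or stopping. Resuming unchanged, which the 0.341 requires, is not among the outcomes named. If the dosage were modified, a fixed 30% rate would no longer be the natural assumption. Section 1.4 also defines feasibility as therapy delivered as planned, which such a trial would not plainly meet.
- The literal reading does not point to one number. It gives 0.885 or 0.341 depending on whether the gates apply, and neither resembles 0.1.

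**Conclusion.** No change to the plan follows. The 0.94 and 0.1 are correct operating characteristics of Rule B: exact values are 0.937 and 0.096, assuming independent participants, a constant event rate, and any Stage 1 or 2 crossing counted as not tolerable. The stage gates support that last assumption.

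The opening condition reads most sensibly as referring to the planned maximum of 25. A reason for mentioning it is visible in section 13.2: with 20 evaluable patients in Stratum 1 and fewer than 5 in Stratum 2, the study closes before Rule B has run its course.

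This is a matter of phrasing. The boundaries, review triggers, 25-participant cohort and feasibility analysis are the same under every reading of the sentence. An analyst who follows the three stages as written reaches the published error rates. If a trial did cross and resume, its report would need to say so, because design-stage probabilities would not describe that course; this limitation is common to staged rules whose early stops go to a review committee.
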